10. PHARMACOKINETIC ENDPOINTS

Investigating the PK of tarextumab in combination with EP is an objective of this study, but a detailed analysis plan is outside the scope of this document. Therefore, no PK analyses are discussed here.

11. SAFETY ENDPOINTS

Analyses of safety endpoints will use data from the safety population. Safety endpoints listed in the study protocol include adverse events (AEs), serious adverse events (SAEs), clinical laboratory parameters, and results from testing for anti-tarextumab antibodies. Other safety endpoints include vital signs and electrocardiogram (ECG) results.

11.1. Treatment Cycles and Dosing

Dosing with tarextumab (or placebo), etoposide and EP will be summarized by the number of cycles of treatment administered (duration of treatment), the number of doses of each study medication, and the extent of exposure to each study medication. Placebo exposure will be summarized in tarextumab-equivalent units, that is, by the number of milligrams of tarextumab the placebo “replaced” during treatment-blinded dosing.

Body surface area (BSA) is determined for each visit. The latest assessment of BSA on or before each visit will be used to determine the protocol-specified amount of drug (mg) in a dose.

11.1.1. Dose Intensity

Dose intensity is defined as the total dose a patient actually received divided by the total dose the patient should have received had there been no missed doses, dosing delays or dosage reductions.

$$\text{Dose intensity} = \frac{\text{Total amount of drug received (mg)}}{\text{protocol-specified, planned amount of drug (mg)}}$$

The actual amount of drug received is obtained from the dosing records.

The protocol specified amount of drug to be received for each treatment is provided below.

Etoposide

The number of doses of Etoposide that should be administered per protocol is

$$3 \cdot \text{floor}\left(\frac{\text{Stop} - \text{Start}}{21}\right) + h_{\text{Etop}}\left[\frac{\text{Stop} - \text{Start}}{21} - \text{floor}\left(\frac{\text{Stop} - \text{Start}}{21}\right)\right],$$

where

$$h_{\text{Etop}}(x) = \begin{cases} 1 & \text{if } 21 \cdot x \geq 0 \\ 2 & \text{if } 21 \cdot x \geq 1 \\ 3 & \text{if } 21 \cdot x \geq 2 \end{cases}$$

Start is the date of the first dose of treatment. Stop is the last dose of treatment.

The amount of drug contained in a dose of Etoposide is

$$100\text{mg} / m^2 \cdot \text{BSA}$$

Carboplatin/Cisplatin/Study Drug

The number of doses of Carboplatin, Cisplatin or Study Drug that should be administered per protocol is

$$1 \cdot \text{floor}\left(\frac{\text{Stop} - \text{Start}}{21}\right) + h\left[\frac{\text{Stop} - \text{Start}}{21} - \text{floor}\left(\frac{\text{Stop} - \text{Start}}{21}\right)\right],$$

where

$$h(x) = \begin{cases} 1 & \text{if } 21 \cdot x \geq 0 \end{cases}$$

Start is the date of the first dose of treatment and Stop is the last dose of treatment for the respective drugs. Treatment period is (last treatment date – first treatment date + 2), allowing 2 extra days to cover any following early visits.

The mg amount of drug contained in a dose of Carboplatin is

$$(\text{AUC of 5}) \times (\text{GFR} + 25)$$

The mg amount of drug contained in a dose of Cisplatin is

$$80\text{mg} / \text{m}^2 \times \text{BSA}$$

The amount of drug contained in a dose of study drug is

$$15\text{mg} / \text{kg} \cdot \text{weight}$$

Weight, BSA and GFR are to be determined at each visit. Use the latest weight, BSA and/or GFR on or before each dose to determine the amount of drug (mg) in a dose.

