On study tumor assessments	Tumor assessments that meet the following criteria: 1. No gap of ≥ 91 days between successive tumor assessments among those on or prior to the on study tumor assessment. (Note: a tumor assessment for which "Not Evaluated" is entered into the database does not qualify as a tumor assessment.) 2. No prior initiation of non-protocol anticancer therapy.
Overall response rate	The proportion of patients achieving a complete response or partial response to treatment.
Dose intensity	The total dose (in mg) a patient actually received divided by the total dose (in mg) the patient should have received had there been no missed doses, dosing delays or dosage reductions.
Intent-to-treat population	All patients randomized to receive study drug regardless of whether they actually received study drug and regardless of whether evidence is found indicating they failed to meet study inclusion/exclusion criteria or had other protocol violations.
Last contact date	The last contact date is the latest assessment/visit date recorded on any of the following case report forms: Discontinuation, Hematology, Chemistry, RECIST Overall Response Tumor Assessments, Survival Follow Up, Study Drug Infusion, Etoposide Infusion or Platinum Therapy Infusion.
Non-Protocol Anti-Cancer Therapy	Non-protocol anti-cancer therapies used by patients during their participation in this study, if any, will be identified by the sponsor after review of relevant data listings.
Per-protocol population	The subset of safety population who either (a) have at least one response evaluation on study, or (b) die prior to their first scheduled response evaluation.
Platinum Therapy / Platinum Choice	The physician's choice of platinum therapy (cisplatin or carboplatin) was used as a stratification variable by the dynamic randomization system. Discrepancies, if any, between the platinum therapy used to stratify a patient's treatment assignment and the platinum therapy actually administered during the study will be dealt with as follows. Platinum choice entered in the dynamic randomization system will be used in all efficacy analyses where platinum choice is included as a model

	effect. However, actual platinum received (as documented on earliest Platinum Therapy Infusion CRF [e.g., Cycle 1, Day 1]) will be used when calculating dosing compliance.

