3.1. Blinded Treatment Phase

Subjects who qualify for enrollment into the phase-2 portion of the study will be randomized in a 1:1 ratio to receive study treatment of EP with placebo or EP with tarextumab. The randomization will be balanced on the choice of platinum therapy (cisplatin versus carboplatin) and the prior use of whole brain radiation (WBR) or prophylactic cranial irradiation (PCI). Changing the choice of platinum therapy is not permitted once the subject is randomized. Treatment for each subject will begin on Cycle 1, Day 1 (the first dosing day). Etoposide 100 mg/m² will be given on Days 1, 2 and 3 and cisplatin 75 mg/m² or carboplatin to an AUC of 5 mg/mL/min will be given on Day 1 of every 21-day cycle for 6 cycles. Subjects may remain in the blinded treatment phase to continue one of the chemotherapy drugs if the other is held or discontinued prior to completing 6 cycles of EP and prior to disease progression. For subjects who have study drug held or discontinued for tolerability reasons, EP chemotherapy should continue to the completion of 6 cycles. Subjects may continue study drug if one or both of the chemotherapy drugs is held or discontinued prior to completing 6 cycles of EP and prior to disease progression.

After the completion of 6 cycles of EP, subjects who do not have disease progression and have not had WBR or PCI prior to study entry and are good candidates for PCI according to the

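### The etoposide planned-dose count in SAP section 11.1.1 ends at the last dose given, so trailing doses omitted in an on-time or early final cycle drop out of the dose-intensity denominator

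*SAP*

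**What the plan says.** Section 11.1.1 divides the dose received by "the total dose the patient should have received had there been no missed doses, dosing delays or dosage reductions"; the Definitions table says the same. Section 3.1 gives the schedule: "Etoposide 100 mg/m² will be given on Days 1, 2 and 3" of each 21-day cycle, for six cycles.

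The etoposide formula is introduced by the words "The number of doses of Etoposide that should be administered per protocol is". It is three times the number of complete 21-day periods between Start and Stop, plus a step function, h_Etop. That function adds 1, 2 or 3 doses when the remainder is at least 0, 1 or 2 days. The end points are defined thus: "Start is the date of the first dose of treatment. Stop is the last dose of treatment".

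The block for carboplatin, cisplatin and study drug adds a further sentence: "Treatment period is (last treatment date – first treatment date + 2), allowing 2 extra days to cover any following early visits". The etoposide block has no such sentence, and the two-day term appears in neither printed formula.

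**The concern.** The number of doses counted as planned in the last cycle depends on the day of the last dose actually given. If treatment stops after Day 1 of a cycle that ran to schedule, the formula treats Days 2 and 3 as never having been due. The definition says missed doses belong in the denominator. A final cycle given slightly early also loses planned doses, although nothing was missed, and the ratio then exceeds 100%.

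The doses affected lie in the cycle in which etoposide stopped, where poor tolerability may show. Etoposide dose intensity is tabulated by arm in Table 14.3.5.3. Comparing tolerability between arms is a phase-2 secondary objective (section 2.2).

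**Working it through.** **Inputs.** Section 3.1 gives 3 doses × 6 cycles = 18. Section 11.1.1 gives planned = 3·floor(d/21) + h(r), where d = Stop − Start in days, r is the remainder after whole 21-day periods, and h is 1, 2 or 3 for r ≥ 0, 1 or 2.

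**Assumptions.** Full dose and constant BSA, so the mg ratio equals the ratio of dose counts. Stop is the last etoposide dose. Where several conditions for h are met, the highest applies.

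**Check of the reading.** The SAP prints no worked figure. Six full on-time cycles have d = 5×21 + 2 = 107, so planned = 15 + 3 = 18, as scheduled. Taking the lowest condition met would give 16, so the highest is evidently meant.

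**On-time cycles, final cycle cut short.**

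| Last dose | d | Planned as printed | Given | As printed | Three per cycle begun |
|---|---|---|---|---|---|
| C1D1 | 0 | 0+1 = 1 | 1 | 100% | 1/3 = 33% |
| C1D2 | 1 | 0+2 = 2 | 2 | 100% | 2/3 = 67% |
| C2D1 | 21 | 3+1 = 4 | 4 | 100% | 4/6 = 67% |
| C3D1 | 42 | 6+1 = 7 | 7 | 100% | 7/9 = 78% |
| C6D1 | 105 | 15+1 = 16 | 16 | 100% | 16/18 = 89% |

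**Early final cycle.**
- All 18 doses given, cycle 6 one day early: d = 106, planned 17, 18/17 = 106%.
- The same, two days early: d = 105, planned 16, 18/16 = 113%.
- Two full cycles, the second two days early: d = 21, planned 4, 6/4 = 150%.
- Cycle 2 two days early and stopped after Day 1: d = 19, planned 0+3 = 3, 4/3 = 133%, against 4/6 = 67%.

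**Cases where omissions do count.**
- Day 2 missed but Day 3 given, in Cycle 1: d = 2, planned 3, 2/3 = 67%. In Cycle 6: d = 107, 17/18 = 94%.
- Cycle 2 one day late, Day 1 only: d = 22, planned 5, 4/5 = 80%. Two days late: d = 23, planned 6, 4/6 = 67%.
- Cycle 6 two days late, Day 1 only: d = 107, 16/18 = 89%.

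**Would the two-day sentence repair it?** Adding 2 to d turns C1D1 only into 3 planned doses, or 33%. The repair is incomplete. With cycle 6 begun one day early and stopped after Day 1, 104 + 2 = 106 gives 17 planned, 16/17 = 94%. Begun two days early, 103 + 2 = 105 gives 16 planned, 16/16 = 100%. The schedule figure is 89% in both cases.

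**The case against.** The strongest reply is that any dose-intensity measure confined to the treated period must stop somewhere. A patient who stops for good after Cycle 1 Day 3 scores 100% on almost any such rule, although 18 doses were scheduled, so 33% for a C1D1 stop is also a convention. That is fair as far as later, never-begun cycles go. It does not cover Days 2 and 3 of a cycle already begun: these are missed doses in the definition's own sense. Nor does it explain a fully dosed patient scoring above 100%.

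The two-day sentence may have been meant for etoposide as well. As placed, it is not tied to that drug, and applying it leaves the early cases above unresolved.

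A reader might infer that Day 2 and Day 3 doses missed in a final cycle never count. The printed formula does not support that: omissions followed by a later dose in the cycle count, and trailing omissions count partly or fully when the cycle began one, or at least two, days late.

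A reader might also infer that the formula conceals poorer tolerability in the tarextumab arm. The SAP gives no frequency of truncated final cycles by arm, so a differential effect is only a possibility. Other outputs also show such intolerance. Section 11.1.2 bases dosing compliance on the protocol schedule, Table 14.3.5.4 counts missed and delayed etoposide doses with reasons, and separate tables cover adverse events leading to delay, reduction or withdrawal of etoposide.

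**Conclusion.** The point holds in this limited form: the printed etoposide count contradicts the SAP's definition whenever trailing doses are omitted in a final cycle that starts on or ahead of the 21-day grid, and it can put a fully dosed patient above 100%. When cycles run on time, at most two doses per patient are lost. That is two of three for a one-cycle patient (67 percentage points) and two of 18 for a six-cycle patient (11 points). The measure is a descriptive exposure summary with no test attached, and efficacy is untouched. The effect on arm-level averages cannot be sized from the SAP. Correction is still worthwhile, because a stated rule yields a wrong reported figure and the change is cheap.

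**What to change.** In section 11.1.1, replace the etoposide expression and drop h_Etop:

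planned etoposide doses = 3 × max[number of etoposide cycles begun per the dosing records, floor((Stop − Start)/21) + 1], with a maximum of 18,

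where Start and Stop are the dates of the first and last etoposide dose. The cap is the SAP's own 3 doses × 6 cycles. State also that the two-day sentence does not apply to etoposide.

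Checks: C1D1 only gives 3 × max(1, 1) = 3. Any stop in cycle 6, early or on time, gives 3 × 6 = 18. A wholly skipped third cycle followed by an on-time fourth gives floor(63/21) + 1 = 4, so 12 planned, and delays amounting to a full cycle still count as the definition requires.

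A shorter formula, 3 × [floor((Stop − Start + 2)/21) + 1], is tempting but counts calendar windows, not cycles. With cycle 6 three days early and stopped after Day 1, floor(104/21) = 4 gives 15 planned and 16/15 = 107%. Three full cycles with 17 days' total delay have d = 42 + 17 + 2 = 61, so floor(63/21) = 3 gives 12 planned before a fourth cycle was due; the recommended rule gives 9.

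Cost: one formula in the SAP and one derivation step using the cycle records. Reported etoposide dose intensity becomes slightly lower for patients with truncated final cycles, and fully dosed patients with an early final cycle return to 100%.

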Subjects may continue one of the chemotherapy drugs if the other is held or discontinued prior to completing 6 cycles of EP and prior to disease progression. Subjects should continue EP alone for a total of 6 cycles if tarextumab is held or discontinued prior to the completion of 6 cycles of EP. Subjects may continue study drug if one or both of the chemotherapy drugs is held or discontinued prior to completing 6 cycles of EP and prior to disease progression.

The phase-2 portion of the study may commence after the safety and tolerability of the highest tolerable dose of tarextumab has been confirmed in both cohorts of subjects with etoposide and cisplatin/carboplatin during phase-1b. The highest tarextumab dose that is tolerable with both platinum options will be used in the phase-2 portion of the study. For example: if tarextumab at 15 mg/kg is tolerable with etoposide and cisplatin, but not tolerable with etoposide and carboplatin; and tarextumab at 12.5 mg/kg is tolerable with etoposide and carboplatin, then tarextumab at 12.5 mg/kg will be the dose used in phase-2. The phase-2 portion includes a blinded treatment phase and follow-up phase. It is a multicenter, randomized, placebo-controlled portion evaluating the efficacy and safety of tarextumab in combination with etoposide and platinum therapy in subjects with previously untreated ES-SCLC. Subjects may be treated with cisplatin or carboplatin as determined by the Investigator prior to randomization. Alteration to the choice of platinum therapy is not permitted once the subject is randomized.

Approximately 135 evaluable subjects will be enrolled to the phase-2 portion of the study. Evaluable subjects are those who received at least one dose of study drug (either tarextumab or placebo).

Version 1.1 of standard response evaluation criteria in solid tumors (RECIST) criteria [Ref-1] was used to evaluate patients' responses to treatment. RECIST response categories include complete response (CR), partial response (PR), stable disease (SD) and progressive disease (PD). In addition to these four primary ratings, a patient's response to treatment is classified as unevaluable (abbreviated NE) when no imaging/measurement is performed at a particular time point.

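### Section 11.1.1 counts planned platinum and etoposide doses with no six-cycle ceiling, so six-cycle completers delayed by about three weeks or more in total are charged with doses the plan does not contain

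*SAP*

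**What the plan says.** The Definitions and section 11.1.1 agree on the denominator. Section 11.1.1 describes it as "the total dose the patient should have received had there been no missed doses, dosing delays or dosage reductions".

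The same section then turns this into a count. For platinum and study drug together, "The number of doses of Carboplatin, Cisplatin or Study Drug that should be administered per protocol is" floor((Stop − Start)/21) + 1, where Start and Stop are the first and last dose of the drug concerned. For etoposide, "The number of doses of Etoposide that should be administered per protocol is" three times the same floor, plus 1, 2 or 3 according to the days left over. Neither formula has an upper limit. Under the platinum and study-drug formula the text adds: "Treatment period is (last treatment date – first treatment date + 2), allowing 2 extra days to cover any following early visits". The printed formula does not contain those 2 days.

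On the length of chemotherapy, section 3.1 says platinum "will be given on Day 1 of every 21-day cycle for 6 cycles", with "Etoposide 100 mg/m² will be given on Days 1, 2 and 3" of each of those cycles. Section 3 keeps the same total when tarextumab is held or stopped: "Subjects should continue EP alone for a total of 6 cycles". Only study drug runs on after chemotherapy (section 3.1).

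**The concern.** One elapsed-time count serves a drug given until progression and a drug given for a fixed course. For study drug, a longer treatment span does mean that more doses were due. For platinum and etoposide it does not: after the sixth cycle nothing more is due, and a later last dose reflects delay alone. The count therefore turns delay into extra planned doses, although the denominator is defined as what was due without delay.

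Comparing safety and tolerability between arms is a phase-2 secondary objective (section 2.2), and the exposure shells tabulate dose intensity by arm for etoposide, cisplatin and carboplatin. A score of 86% or 75% would normally be read as chemotherapy withheld or reduced. Here it can belong to a patient who received every planned dose in full.

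**Working it through.** **Inputs from the SAP.** Six cycles of 21 days; one platinum dose per cycle, so 6; three etoposide doses per cycle, so 18 (section 3.1). Count formulas and the 2-day allowance from section 11.1.1.

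**Assumption.** Total delay over the course, D days, is not given in the SAP, so a range is run. Milligrams per dose are held constant.

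**Spans for a six-cycle completer.** Platinum, cycle 1 day 1 to cycle 6 day 1: 5 × 21 + D = 105 + D. Etoposide, cycle 1 day 1 to cycle 6 day 3: 107 + D.

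**Reproducing the planned course (D = 0).** Platinum: floor(105/21) + 1 = 6. Etoposide: 107 = 5 × 21 + 2, so 3 × 5 + 3 = 18. Both match the six-cycle plan.

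**With delay, all six cycles given in full:**

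| D (days) | Platinum planned, as printed | 6/planned | Platinum planned, with +2 | 6/planned | Etoposide planned, as printed | 18/planned |
|---|---|---|---|---|---|---|
| 0 | 6 | 100% | 6 | 100% | 18 | 100% |
| 18 | 6 | 100% | 6 | 100% | 18 | 100% |
| 19 | 6 | 100% | 7 | 85.7% | 19 | 94.7% |
| 20 | 6 | 100% | 7 | 85.7% | 20 | 90.0% |
| 21 | 7 | 85.7% | 7 | 85.7% | 21 | 85.7% |
| 40 | 7 | 85.7% | 8 | 75.0% | 22 | 81.8% |
| 42 | 8 | 75.0% | 8 | 75.0% | 24 | 75.0% |

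Example, platinum at D = 21: floor(126/21) + 1 = 7.

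**Effect of the missing 2 days.** If the sixth platinum dose comes one day early, the span is 104 days. As printed, floor(104/21) + 1 = 5, and 6/5 = 120%. With the allowance, floor(106/21) + 1 = 6, and 6/6 = 100%.

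**Cisplatin in milligrams.** The table gives dose-count ratios. Section 11.1.1 uses 80 mg/m² in the cisplatin denominator, whereas section 3.1 gives 75 mg/m² for phase 2. If 75 is given and divided by 80, the ratio is 75/80 = 93.8% with no delay, 93.75% × 6/7 = 80.4% with seven planned doses and 93.75% × 6/8 = 70.3% with eight. That is a separate contradiction, and the passages must be reconciled.

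**Effect of a cap at 6 and 18.** A completer scores 100% at any delay. A patient stopped after two on-time cycles scores 2/2 = 100% with or without the cap. With 21 days of total delay, a patient stopped after four platinum doses scores 4/(floor(84/21) + 1) = 4/5 = 80%, and after five 5/(floor(105/21) + 1) = 5/6 = 83.3%.

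**The case against.** The strongest reply is that dose intensity ought to fall with delay. A rate per unit time for a completer is 126/(126 + D), which gives 126/147 = 85.7% at 21 days and 126/168 = 75.0% at 42 days, the same values as the formula. On that view the formula counts the doses that would fit into the time the patient was treated.

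This shows what may have been intended, but it does not rescue the text. The SAP defines a ratio of total doses against what was due without delay, not a rate. Nor does the platinum count behave as a rate: as printed it gives 100% at 20 days, where the rate is 126/146 = 86.3%, and then drops by a whole cycle at 21 days.

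Other parts of the reply stand:

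- Dosing compliance (section 11.1.2) refers to the protocol schedule, not to this count, so a completer scores 100% there unless the count is reused.
- The shells already show cycles, infusions, total milligrams, duration and delayed doses.
- The 120% figure disappears once the 2-day sentence is applied. What remains is that the printed formula and the text disagree.
- The full score of a patient who stops early on time comes from taking Stop as the last dose. A cap does not change it.

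Three stronger inferences are tempting, and the SAP supports none of them. A reader might infer that the comparison between arms will be biased, but the same formula applies to both arms, no delay data are given and the exposure tables carry no test. A reader might infer that ordinary delays trigger the extra cycle; 4 days in each of the five intervals makes 20, which is short of 21 as printed and past 19 only with the +2. And it is not generally true that 20 days costs nothing: that holds for platinum as printed, but etoposide is already at 90.0%.

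**Conclusion.** The point holds for dose intensity of platinum and etoposide. The uncapped count contradicts both the six-cycle plan and the SAP's definition of the denominator, and no other section supplies a limit. For a patient given six full cycles, platinum falls to 85.7% from 21 days of total delay and to 75.0% from 42 days, or from 19 and 40 days with the +2. Etoposide as printed begins to fall at 19 days and reaches the same two values at 21 and 42 days.

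These are dose-count ratios with constant milligrams per dose. Shorter delays leave completers at 100%. The frequency is unknown because the SAP gives no delay distribution. Only the descriptive dose-intensity rows are affected; no efficacy or adverse-event analysis uses them. The uncapped count is not contradicted for study drug.

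**What to change.** In section 11.1.1, to match the stated definition:

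- Set planned platinum doses to min{6, floor((Stop − Start + 2)/21) + 1} and limit planned etoposide doses to 18.
- Leave the study-drug count uncapped.
- Print the 2 days in the formula they belong to, and say whether they also apply to etoposide, since the sentence stands only under the platinum and study-drug formula.
- State that dose intensity is a total-dose ratio, and that delay in completers is read from the delayed-dose and duration rows already in the shells.

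If the sponsor wants a rate instead, replace the step count with dose per unit time and change the definition in both places.

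The cost is a short text change and a small change to the program. The cap has a real downside: delay no longer lowers a completer's score but still lowers that of patients who stop before cycle 6, and an early stopper without delay still scores 100%. The dose-intensity rows must therefore be read together with the number of cycles administered, and a footnote in the shells should say so.

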investigator should receive PCI within 8 weeks after the last dose of chemotherapy at a total dose of 25 Gy in 10 fractions. If subjects discontinue EP with treatment-related toxicities prior to completing 6 cycles and are good candidates for PCI per the investigator, PCI can be initiated at any time determined appropriate by the investigator. Subjects who do not receive PCI within 8 weeks after the last dose of chemotherapy can have PCI later during the study as determined by the investigator. Study drug (tarextumab or placebo) administration should continue at every 21-day cycle between the completion of chemotherapy and the initiation of PCI. PCI should not be initiated within 2 weeks of study drug administration and study drug will be held during the PCI treatment period. Subjects will resume study drug alone ≥ 14 days after completion of PCI, until disease progression or unacceptable treatment-related toxicities or withdrawal of consent. Subjects will discontinue study treatment if there is evidence of central nervous system (CNS) metastasis.

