11.1.2. Dosing Compliance

Dosing compliance is defined as the ratio of the number of doses administered to the number of doses planned according to the schedule outlined in the study protocol.

$$\text{Dosing compliance} = \frac{N_{\text{administered}}}{N_{\text{planned}}} \times 100\%$$

where N_{planned} is the number of doses planned according to the schedule outlined in the study protocol and $N_{\text{administered}}$ is the number of doses the patient received.

Dosing compliance will be summarized as a continuous variable (see Section 5) and by the numbers of patients with 0% to <20%; 20% to <40%; 40% to <60%; 60% to <80%; 80% to <100%; and 100% compliance. The reasons for delaying and/or withholding doses randomized study drug, selected platinum agent and etoposide will also be summarized.

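### Study-drug dose intensity counts 21-day cycles through the PCI hold that section 3.1 requires, so patients who resume after PCI usually score below 100% for following the plan

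*SAP*

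**What the plan says.** Section 11.1.1 defines dose intensity as the dose received "divided by the total dose the patient should have received had there been no missed doses, dosing delays or dosage reductions". It labels the denominator as the protocol-specified amount. For study drug the count is introduced with "The number of doses of Carboplatin, Cisplatin or Study Drug that should be administered per protocol is", followed by floor((Stop − Start)/21) plus a term that always equals 1. Of the two dates it says "Start is the date of the first dose of treatment and Stop is the last dose of treatment for the respective drugs". The only allowance is a treatment period lengthened by 2 days, "allowing 2 extra days to cover any following early visits"; the text does not say whether those 2 days enter the formula.

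Section 3.1 sets the study-drug schedule around PCI. Before PCI, "Study drug (tarextumab or placebo) administration should continue at every 21-day cycle between the completion of chemotherapy and the initiation of PCI". Then "PCI should not be initiated within 2 weeks of study drug administration and study drug will be held during the PCI treatment period". Afterwards, "Subjects will resume study drug alone ≥ 14 days after completion of PCI", with no latest date. PCI is given in 10 fractions.

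Section 11.1.2 adds a second exposure measure, which refers to the protocol: "Dosing compliance is defined as the ratio of the number of doses administered to the number of doses planned according to the schedule outlined". It gives no formula for the planned number.

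**The concern.** A denominator described as what the protocol specifies should not contain doses that the protocol schedule excludes. The hold is part of that schedule. It is neither a missed dose nor a delay, which are the departures that dose intensity is meant to charge. Yet the formula plans a dose every 21 days straight through it.

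The ordering of patients also suffers. One who stops for good at PCI has Stop before the hold, so none of it enters the denominator. One who resumes as instructed carries the whole hold. Dose intensity is reported by arm in Table 14.3.5.1, and comparing tolerability between arms is a phase-2 secondary objective (section 2.2). If the arms differ in the share who resume after PCI, part of any difference in dose intensity would come from the formula.

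**Working it through.** **Inputs from the SAP.** Planned doses = floor((Stop − Start)/21) + 1 (section 11.1.1). Hold: at least 14 days from last dose to PCI, no drug during 10 fractions, at least 14 days after PCI (section 3.1). Hazards of 0.1386 (control) and 0.0901 (tarextumab) per month for months 0 to 5 (Table 3).

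**Assumptions.** Doses and fractions fall on weekdays, so 10 fractions take 11 to 13 days from first to last. PCI starts 14 to 21 days after the last dose. Doses are full and weight is stable, so dose intensity equals doses given divided by doses planned.

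**Control.** The SAP states no dose-intensity figure to reproduce. On an uninterrupted 21-day schedule, 6, 8 or 12 doses give 6, 8 or 12 planned, with or without the 2 extra days. The score is 100%, so any shortfall below comes from the hold.

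**Length of the gap.** Shortest: 14 + 11 + 14 = 39 days. Longest when drug resumes exactly 14 days after PCI: 21 + 13 + 14 = 48 days. Longest when it resumes within 28 days: 21 + 13 + 28 = 62 days.

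**Doses charged.** With n doses given and one gap of g days, Stop − Start = 21(n − 2) + g, so planned = n − 1 + floor(g/21). One dose too many is planned from g = 42, two from g = 63. If the 2 extra days are added, the thresholds are 40 and 61.

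| Doses given | Gap 42–60 days | Gap 63 days |
|---|---|---|
| 8 | 8/9 = 88.9% | 8/10 = 80.0% |
| 10 | 10/11 = 90.9% | 10/12 = 83.3% |
| 12 | 12/13 = 92.3% | 12/14 = 85.7% |

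Gaps of 39 to 41 days leave the score at 100% under the printed formula if nothing else slipped. At 39 days, 3 days of delay elsewhere are enough to lose a dose.

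**How often the threshold is reached.** Listing the compliant weekday timings with equal weight, 83% reach 42 days if drug resumes exactly 14 days after PCI, and 98% if it resumes 14 to 28 days after. For 40 days the shares are 97% and over 99%. These are shares of possible calendars, not forecasts of practice.

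**Patients who stop at PCI.** After 6, 7 or 8 full doses on schedule: 6/6, 7/7 or 8/8 = 100%.

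**Difference between arms.** Six cycles take 126 days = 4.14 months. Event-free at that point: exp(−0.1386 × 4.14) = 0.563 for control and exp(−0.0901 × 4.14) = 0.689 for tarextumab, a difference of 0.126. If all of these patients had PCI and resumed, the difference in mean dose intensity would be:

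- gap 42–60 days: 0.126 × 7.7 to 0.126 × 11.1 = 1.0 to 1.4 points;
- gap 63 days: 0.126 × 14.3 to 0.126 × 20.0 = 1.8 to 2.5 points.

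**The case against.** Charging all elapsed time between first and last dose is a simple convention, and the definition does refer to an absence of dosing delays. Dose intensity is one descriptive block without a p-value. Tolerability is also shown by adverse events leading to delay, reduction or withdrawal, by missed and delayed doses with reasons, and by Listings 16.2.5.4 and 16.2.8.15. This limits the consequence. It does not rescue the formula, because section 11.1.1 presents the count as per protocol and section 3.1 makes the hold part of the protocol.

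Three stronger readings are tempting and not supported:

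- **A PFS benefit would appear as poorer tolerability.** Even with every event-free patient having PCI and resuming, the Table 3 figures give about 1 to 2.5 points. PCI is meant for good candidates without earlier cranial irradiation, so the difference is probably smaller.
- **The 56% and 69% event-free figures are the upper bound on who has PCI.** Section 3.1 also allows PCI after early discontinuation of chemotherapy for toxicity, so they describe only those who could reach PCI after six cycles.
- **Sections 11.1.1 and 11.1.2 contradict each other.** Section 11.1.2 points to the protocol schedule without a count. That this schedule leaves out the hold is an inference from section 3.1; it could be the nominal 21-day schedule. What stands is that the planned count for compliance is undefined.

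**Conclusion.** The point holds. The study-drug denominator includes doses that section 3.1 does not allow. An affected patient usually loses one dose, for example 89% with 8 doses given or 92% with 12, and loses two at gaps of 63 days or more. This rests on weekday fractions and full doses at stable weight.

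It would be wrong to infer that every patient who follows the rule is under-scored, since the shortest gaps escape. It would also be wrong to infer that everyone who stops at PCI scores 100%, since that needs earlier doses to have been full and on time. No efficacy analysis is touched. The PCI rate is not given, so the effect on the comparison of arms can only be bracketed: probably about 1 to 2 points, against the arm with more patients who resume. The correction is worth making because a stated rule gives a wrong number and is cheap to put right.

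**What to change.** Reconcile section 11.1.1 with section 3.1 by removing only the hold that section 3.1 itself requires. No dose or clinical rule changes. For patients who resume study drug after PCI:

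planned doses = [floor((A − Start)/21) + 1] + [floor((Stop − B)/21) + 1]

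where A is the later of the last pre-PCI dose and PCI start minus 14 days, and B is PCI end plus 14 days, the earliest resumption section 3.1 allows. Patients with no dose after PCI keep the current formula.

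Cutting instead from the last pre-PCI dose to the first post-PCI dose would drop the whole gap whatever its length, and hide real delays. With A and B, delay beyond the required hold stays in. Take 6 doses before PCI and 2 after, PCI starting 14 days after the sixth dose and lasting 11 days:

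- Resumption 14 days after PCI: 6 + 2 = 8 planned, 8/8 = 100%.
- Resumption 38 days after PCI (gap 14 + 11 + 38 = 63 days): Stop − B = 24 + 21 = 45, so 6 + 3 = 9 planned, 8/9 = 88.9%. The printed formula gives 8/10 = 80.0%.

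If a patient resumes before B, which is a deviation, set B to the date of that dose so that the planned count does not fall too low. State whether the 2 extra days enter the formula, and that the same planned count serves study-drug compliance in section 11.1.2.

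The cost is a few lines of SAP text and programming. PCI start and stop dates are already in Listing 16.2.8.15.
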